2.0 Background

2.1 The Diseases

- a. Myelodysplastic syndrome (MDS) is a marrow disorder characterized by paradoxical peripheral cytopenias and a hyperplastic marrow, usually in elderly patients (median age 65 years).¹ Exposure to carcinogens and a high frequency of cytogenetic abnormalities are generally observed.^{2,3} The pathophysiology of the disease appears to be an initial increase in apoptosis of the primitive stem cells with compensatory marrow proliferation, and later escape of clonal disease with malignant potential for transformation to acute leukemia.^{1,4,5} Overall, 50% of patients transform to AML, while the others die of complications of cytopenias (infections, bleeding) while in MDS phase.¹ MDS is divided into low-risk and high-risk. Low-risk MDS includes refractory anemia (RA) and RA-sideroblastic (RA-S) by the French-American-British (FAB) classification and low or intermediate -1 risk by the International Prognostic Scoring System (IPSS). High-risk MDS (usually marrow blasts $\geq 10\%$) includes RA with excess blasts (RAEB) and RAEB in transformation (RAEB-T) by FAB and intermediate –2 or high risk by IPSS.⁶ Median survival in low-risk MDS is 3-4 years, and in high-risk MDS 12 months or less.^{7,8}

There is no current uniformly accepted standard treatment for MDS. Low-risk MDS is usually observed and later treated according to complications with red cell or platelet transfusions, antibiotics, and growth factors (EPO, G-CSF). Investigational studies include amifostine, thalidomide, TNF- α inhibitors (e.g. Enbrel), Mylotarg, arsenic trioxide and hypomethylating agents.^{9,10} High-risk MDS is usually treated with investigational therapies including AML regimens, topotecan + ara-C, above investigational strategies, and allogeneic stem cell transplant.¹⁰⁻¹² Recently, 5-azacytidine and decitabine have been FDA approved for use in appropriately selected patients. Results have included improved responses (both clinical and cytogenetic), better quality of life, but no statistically significant survival advantage. Additionally, lenalidomide has also been FDA approved for use in patients with the 5q- syndrome, with an improvement in red blood cell transfusion dependence as well as cytogenetic response. MDS affects 12,000 to 20,000 individuals in the USA yearly. RAS mutations occur in 30% to 65% of MDS cases.^{13,14}

- b. AML: Prognosis in AML in adults has improved modestly. With modern regimens, including anthracyclines plus cytarabine, the CR rates are 60% to 70% and the cure rates are 15% to 25%. Prognosis is related to 1) leukemia karyotype, 2) patient age, and 3) performance and organ functions. Patients with t(8;21), inversion 16 or t(15;17) have CR rates of

90% and cure rates of 50% to 80%. Younger patients (age \leq 50 years) with diploid karyotypes have CR rates of 70% to 80% and cure rates of 20% to 25%. Older patients and those with adverse karyotypes have CR rates of 35% to 50% and cure rates of 10% or less. Elderly patients with AML have a poor prognosis. This is due in part to the poor tolerance to therapy, and also the higher frequency of poor prognostic features, such as high-risk cytogenetic abnormalities and MDR expression. The experience at M.D. Anderson from 1996 to 2000 for patients age 65 years or older is a clear example of this poor prognosis. We treated 245 patients in this age group during this period. CR was achieved in 118 (48%) while induction mortality (i.e., death within 7 weeks from the start of chemotherapy) occurred in 54 (22%). 38 patients (18%) were alive in CR after 1 year, and 16 (8%) at 2 years.^{15,16}

2.2 Maintenance therapy in MDS and AML

The role of post-remission therapy has been fully established in treating adult patients with AML. Several older studies have suggested that there is no role for maintenance therapy in AML. An ECOG study randomized patients after receiving standard induction therapy into 2 arms; one receiving 2 further courses of attenuated induction followed by maintenance, versus maintenance therapy only for 2 years. This study demonstrated that a more intensive post-remission therapy is necessary and questioned the role of maintenance. A randomized CALGB study demonstrated that protracted maintenance for 36 months was not superior to 8 months of maintenance and led to further questioning of role of maintenance. Other studies have also questioned the benefit of maintenance therapy.

On the other hand, several studies have convincingly demonstrated the benefit of maintenance therapy in older adults. A study by the German AML cooperative group patients achieving CR after receiving a standard induction regimen were randomized to receive either a protracted maintenance therapy or 'observation only'. Disease free survival at 3 years was 30% versus 17% ($p=0.003$) in favor of the maintenance arm. As a result of this study, maintenance therapy has been established as an integral part of front-line therapy in AML patients by the German group. Other studies, including studies by SWOG and Japanese adult leukemia study group (JALSG) have confirmed the benefit of maintenance.

Therefore, although maintenance therapy is clearly effective its precise role has not been well defined. Maintenance therapy is likely to be beneficial in older adults with high-risk disease and is less likely to be effective in younger adults who are able to tolerate more intensive forms of post-remission therapy. An important factor in considering post-remission therapy in older adults with AML is the availability of an effective

and non-toxic regimen. Studies of interleukin- 2 (IL-2) in the maintenance setting of AML were largely unsuccessful particularly due to the difficulty in delivering the drug due to its significant toxicity.

PD-1 is a negative co-stimulatory receptor on activated T lymphocytes, which counters the activation signal provided by TCR ligation.^{17a} PD-1 can also be induced in natural killer cells, B cells and monocytes. The two ligands of PD-1 are PD-L1 and PD-L2. They have distinct cellular expression patterns. Expression of PD-L2 is largely restricted to antigen presenting cells while PD-L1 is broadly expressed in tissues and can be further induced by exposure to interferon IFN- γ .^{17a} PD-L1 is the major ligand for PD-1-mediated immune-suppression. Increased evidence suggests that PD-L1 expression on solid tumor cells is capable of dampening antitumor immune responses, and blockade of PD-L1 inhibits tumor growth and delays progression in murine models.^{17a} Yang and colleagues have demonstrated that PD-1 and its two ligands, PD-L1 and PD-L2, as well as CTLA4, are aberrantly upregulated in 8–34% of bone marrow CD34+ cells from patients with myeloid leukemias.^{18a} Tumor cells may suppress the function of tumor infiltration T cells by modulating PD-1. PD-1 has been reported to be upregulated on tumor infiltration T cells in melanoma and lung cancer.¹⁷ In AML and MDS bone marrow biopsies, it has been reported that blasts are positive for PD-L1 whereas stroma/non-blast cellular compartment are positive for PD-1. Therefore, PD-1 ligands expressed on tumor cells may act through PD-1-positive stroma within the tumor microenvironment of AML and MDS patients.^{18a}

In another study, Zhang, et al using the murine leukemia cell line, C1498 showed that when transferred intravenously into immunocompetent mice, C1498 cells grew progressively and apparently evaded immune destruction.(19a) Low levels of PD-L1 expression were found on C1498 cells grown in vitro. However, PD-L1 expression was up-regulated on C1498 cells when grown in vivo. PD-1(-/-) mice challenged with C1498 cells generated augmented antitumor T-cell responses, showed decreased AML burden in the blood and other organs, and survived significantly longer than did wild-type mice. Similar results were obtained with a PD-L1 blocking antibody.(19a) These data suggest the importance of the PD-1/PD-L1 pathway in immune evasion in AML, providing a rationale for clinical trials targeting this pathway in leukemia patients.

We propose to investigate nivolumab in patients with high-risk MDS and AML as maintenance following achievement of complete remission after induction with idarubicin and cytarabine. In the phase I portion of the trial, the aim is to define the tolerability of the administration of Nivolumab after achieving CR. In the phase II portion of the trial, the event free survival in newly diagnosed patients

with AML and high-risk MDS ($\geq 10\%$ blasts) will be determined and compared to historical controls.

2.3 The Treatment

PD-1 (or CD279), a 55-kd type 1 transmembrane protein, is a member of the CD28 family of T-cell costimulatory receptors that include immunoglobulin superfamily members CD28, CTLA-4, inducible co-stimulator (ICOS), and B and T-lymphocyte attenuator (BTLA). PD-1 is highly expressed on activated T cells and B cells. PD-1 expression can also be detected on memory T-cell subsets with variable levels of expression. Two ligands specific for PD-1 have been identified: PD-L1 (also known as B7-H1 or CD274) and PD-L2 (also known as B7-DC or CD273). PD-L1 and PD-L2 have been shown to down-regulate T-cell activation upon binding to PD-1 in both murine and human systems.^{15,16,17} The interaction of PD-1 with its ligands, PD-L1 and PD-L2, that are expressed on antigen-presenting cells (APC) and dendritic cells (DC), transmits negative regulatory stimuli to down-modulate the activated T-cell immune response. The absence or inhibition of PD-1 in murine models has resulted in the development of various autoimmune phenotypes and autoimmune diseases.¹ Taken together, these results suggest that inhibition of PD-1 binding to its ligands has the potential to activate T-cell responses. Since these responses are variable and dependent upon various host genetic factors, PD-1 deficiency or inhibition is not accompanied by a universal loss of tolerance to self antigens.

Tumors can express tumor-specific antigens as a result of mutational burden and ongoing immune surveillance is believed to control the development of many tumors. Tumor progression may depend upon acquisition of mechanisms which permit them to evade an effective immune response. One such mechanism of evasion may be the expression of ligands which engage inhibitory receptor(s) on anti-tumor T-cells of many tumors. PD-L1 expression has been found on a number of tumors, and may be a mechanism by which tumors can directly engage PD-1 to evade an effective anti-tumor immune response.^{18,19,20}

Expression of INF- γ by T-cells is known to induce PD-L1 expression in tumors.²¹ PD-L1 expression has been associated with poor prognoses in renal,^{22,23,24} esophageal,²⁵ gastric,²⁶ ovarian,²⁰ pancreatic,²⁷ and lung cancer.²⁸ PD-1 engagement on T-cells by PD-L1+ APC or PD-L1+ tumor cells in the tumor microenvironment may limit effective immune responses. In contrast to the findings above,

PD-L1 expression may result from CD3+ T-cell infiltration into tumors, which was observed to be a positive prognostic factor. Co-localization of lymphoid cell infiltrates and PD-L1 staining has been observed in human melanoma lesions.²⁹ More recent data have implicated the role of PD-1 in human infections, particularly in HCV³⁰ and human immunodeficiency virus (HIV).³¹ In these cases, high expression levels of PD-1 have been found in viral-specific CD8+ T-cells that also display a non-responsive or exhausted phenotype. The observation that PD-1 expression is reduced in antigen loss variants of the target

epitope of PD-1 high antigen-specific T-cells is consistent with the chronic stimulation hypothesis.⁸ Non-responsive PD-1 high T-cells have been observed in simian immunodeficiency virus (SIV) infection in rhesus macaques. More important, treatment of SIV-infected macaques with an anti-PD-1 mAb (3 mg/kg x4) resulted in decreased viral loads and increased survival along with expanded T-cells with increased T-cell functionality.⁴ These studies have led to anti-PD-1 testing in tumor models.

Studies in multiple tumor models using a chimeric murine anti-mouse PD-1 antibody showed that PD-1 blockade has anti-tumor activity (Section 4.1.3).³² Blocking PD-1 in PD-L1+ tumors may reverse the inactivation of tumor-specific effector T-cells at the tumor site as well activate anti-tumor responses that are limited by PD-L1 expression on “host” DC or APC. The anti-tumor effects of anti-PD-1 observed in several murine models suggest that both PD-L1+ and PD-L1- tumors may be targeted using this approach. In addition, in several tumor models in which anti-PD-1 has proved ineffective, PD-1 blockade can be combined with vaccines or other immunomodulatory antibodies for improved therapeutic efficacy.^{33,34,35} PD-1 blockade by nivolumab is a promising avenue to pursue as an anti-tumor therapy for recurrent or treatment-refractory malignancies or as an anti-viral therapy for chronic viral infections.

3.0 Objectives

- 3.1 **For phase I portion of study:** To determine the tolerability of the combination of idarubicin, cytarabine (ara-C), and nivolumab (IAN) in patients with high-risk MDS and AML.
- 3.2 **For phase II portion of study:** To determine event-free survival (EFS) where the events is defined as death or relapse using the combination of idarubicin, cytarabine, and nivolumab in patients with high-risk Myelodysplastic syndrome (MDS) and Acute Myeloid Leukemia (AML).

4.0 Patient Eligibility

Inclusion Criteria:

- 4.1 Diagnosis of 1) AML (WHO classification definition of $\geq 20\%$ blasts), or 2) high risk MDS (defined as the presence of 10% blasts).
- 4.2 Patients aged 18 to 60 years are eligible. Patients older than 60 who are deemed fit to receive intensive chemotherapy by the treating physician are eligible after discussion with the PI.
- 4.3 In the Phase I portion, patients with relapsed or refractory AML/MDS are also eligible, as per the treating physician’s discretion.

- 4.4 For the Phase II portion of the study, patients must be chemo-naïve, i.e. not have received any prior chemotherapy (except hydrea or one dose of ara-C ≤ 2g) for AML or MDS. They could have received hypomethylator agents, transfusions, hematopoietic growth factors or vitamins. Temporary prior measures such as apheresis or hydrea or one dose of ara-C ≤ 2g are allowed in order to safely control hyperleucocytosis prior to enrollment.
- 4.5 Serum biochemical values with the following limits unless considered due to leukemia:
 - creatinine \leq 1.5 mg/dl
 - total bilirubin \leq 1.5 mg/dL, unless increase is due to hemolysis or congenital disorder
 - transaminases (SG PT) \leq 2.5x ULN
- 4.6 Ability to take oral medication.
- 4.7 Ability to understand and provide signed informed consent.
- 4.8 Baseline test of ejection fraction must be \geq 50%.
- 4.9 Performance status <3, unless directly related to disease process as determined by the Principal Investigator

Exclusion Criteria:

- 4.10 Subjects with APL.
- 4.11 Any coexisting medical condition that in the judgment of the treating physician is likely to interfere with study procedures or results.
- 4.12 Nursing women, women of childbearing potential with positive urine pregnancy test, or women of childbearing potential who are not willing to maintain adequate contraception (such as birth control pills, IUD, diaphragm, abstinence, or condoms by their partner) over the entire course of the study.
 - Women of childbearing potential (WOCBP) must use appropriate method(s) of contraception. *WOCBP should use an adequate method to avoid pregnancy for 23 weeks (30 days plus the time required for nivolumab to undergo five half-lives) after the last dose of investigational drug*
 - Women of childbearing potential must have a negative serum or urine pregnancy test (minimum sensitivity 25 IU/L or equivalent units of HCG) within 24 hours prior to the start of nivolumab
 - Women must not be breastfeeding

- Men who are sexually active with WOCBP must use any contraceptive method with a failure rate of less than 1% per year *Men receiving nivolumab and who are sexually active with WOCBP will be instructed to adhere to contraception for a period of 31 weeks after the last dose of investigational product Women who are not of childbearing potential (ie, who are postmenopausal or surgically sterile as well as azoospermic men do not require contraception*

4.13 Cardiac disease: Congestive heart failure > class II NYHA. Patients must not have unstable angina (anginal symptoms at rest) or new onset angina (began within the last 3 months) or myocardial infarction within the past 6 months.

4.14 History of cardiac ventricular arrhythmias requiring anti-arrhythmic therapy within past 3 months.

4.15 Thrombotic or embolic events such as a cerebrovascular accident including transient ischemic attacks within the past 6 months.

4.16 Pulmonary hemorrhage/bleeding event \geq CTCAE Grade 2 within 4 weeks of first dose of study drug.

4.17 Major surgery, open biopsy or significant traumatic injury within 4 weeks of first study drug.

4.18 Active clinically serious and uncontrolled infection > CTCAE Grade 2 uncontrolled with antibiotics

4.19 Patients should be excluded if they have an active, known or suspected autoimmune disease. Subjects are permitted to enroll if they have vitiligo, type I diabetes mellitus, residual hypothyroidism due to autoimmune condition only requiring hormone replacement, psoriasis not requiring systemic treatment, or conditions not expected to recur in the absence of an external trigger

4.20 Patients should be excluded if they are known to be positive test for hepatitis B virus surface antigen (HBV sAg) or hepatitis C virus ribonucleic acid (HCV antibody) indicating acute or chronic infection

4.21 Patients should be excluded if they have known history of testing positive for human immunodeficiency virus (HIV) or known acquired immunodeficiency syndrome (AIDS)

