5.0 Treatment Plan

5.1 **General:** All patients should be registered with PDMS. Information pertaining to important prognostic factors such as age, performance status and prior therapy will be recorded.

5.2 **Treatment Schedule:** (Each cycle is approximately 28-35 days)

a. **Phase I**

Nivolumab dosed as indicated below starting approximately on day 24 ± 2 days

Idarubicin 12 mg/m² IV over 15 to 30 minutes daily x 3 (days 1-3)

ara-C 1.5 g/m² IV over 24 hours daily (days 1-4)

Solumedrol 50 mg or dexamethasone 10 mg IV daily for 3-4 days with ara-C (days 1-4)

All patients may receive a second induction course at the discretion of treating physician.

The dose of investigational agent, that is, Nivolumab, will be escalated in successive cohorts of patients. Patients will be entered sequentially to each dose level. If none of the first 3 patients at a dose level experience first cycle dose-limiting toxicity (DLT), new patients may be entered at the next higher dose level. If 1 of 3 patients experience first cycle DLT, up to 3 more patients are started at that same dose level. If 1 of 6 experience DLT, then new patients may be entered at the next higher dose level. If 2 or more experience first cycle DLT, no further patients are started at that dose. The MTD is the highest dose level in which <2 patients of 6 develop first cycle DLT. The following table lists out the 3 dosage levels that will be used in the study, and the starting dose is 1mg/kg IV of Nivolumab. There will be no intra-patient dose escalation for Nivolumab.

The enrollment of participants will be staggered; all the participants in each cohort will be observed for approximately 3 weeks from the first dose of Nivolumab before proceeding to the next cohort.

Dose of nivolumab will be as follows:

Dose level	Nivolumab (mg/kg IV)	No of patients
-1	0.3	3
0	1	3
1	3	3

b. **Phase II** (Each cycle is approximately 28-35 days)

Patients will receive 1 or 2 induction cycles of therapy according to the following starting schedule:

Nivolumab starting approximately on day 24 \pm 2 days at a dose defined by Phase I portion of the study but it is expected that the dose 3 mg/kg will be selected based on prior studies.

Idarubicin 12 mg/m² IV over 15 to 30 minutes daily x 3 (days 1-3)

ara-C 1.5 g/m² IV over 24 hours daily (days 1-4) (days 1-3 for patients older than 60)

Solumedrol 50 mg or dexamethasone 10 mg IV daily for 3-4 days with ara-C (days 1-4) (days 1-3 for patients older than 60).

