- Subjects with baseline Grade 1 AST/ALT or total bilirubin who require dose delays for reasons other than a 2-grade shift in AST/ALT or total bilirubin may resume treatment in the presence of Grade 2 AST/ALT OR total bilirubin
- Subjects with combined Grade 2 AST/ALT AND total bilirubin values meeting discontinuation parameters (Discontinuation Section below) should have treatment permanently discontinued
- Drug-related pulmonary toxicity, diarrhea, or colitis, must have resolved to baseline before treatment is resumed
- Drug-related endocrinopathies adequately controlled with only physiologic hormone replacement may resume treatment

If the criteria to resume treatment are met, the subject should restart treatment at the next scheduled timepoint per protocol. However, if the treatment is delayed past the next scheduled timepoint per protocol, the next scheduled timepoint will be delayed until dosing resumes.

If treatment is delayed > 6 weeks, the subject must be permanently discontinued from study therapy, except as specified in discontinuation section.

Nivolumab Discontinuation Criteria:

Treatment should be permanently discontinued for the following:

- Any Grade 2 drug-related uveitis or eye pain or blurred vision that does not respond to topical therapy and does not improve to Grade 1 severity within the re-treatment period OR requires systemic treatment
- Any Grade 3 non-skin, drug-related adverse event lasting > 7 days, with the following exceptions for drug-related laboratory abnormalities, uveitis, pneumonitis, bronchospasm, diarrhea, colitis, neurologic adverse event, hypersensitivity reactions, and infusion reactions:
 - Grade 3 drug-related uveitis, pneumonitis, bronchospasm, diarrhea, colitis, neurologic adverse event, hypersensitivity reaction, or infusion reaction **of any duration** requires discontinuation
- Grade 3 drug-related laboratory abnormalities do not require treatment discontinuation except those noted below:
 - Grade 3 drug-related thrombocytopenia > 7 days or associated with bleeding requires discontinuation
 - Any drug-related liver function test (LFT) abnormality that meets the following criteria require discontinuation:
 - AST or ALT > 8 x ULN
 - Total bilirubin > 5 x ULN
 - Concurrent AST or ALT > 3 x ULN and total bilirubin > 2 x ULN

- Any Grade 4 drug-related adverse event or laboratory abnormality, except for the following events which do not require discontinuation:

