 - Isolated Grade 4 amylase or lipase abnormalities that are not associated with symptoms or clinical manifestations of pancreatitis and decrease to < Grade 4 within 1 week of onset.
 - Isolated Grade 4 electrolyte imbalances/abnormalities that are not associated with clinical sequelae and are corrected with supplementation/appropriate management within 72 hours of their onset
- Any dosing interruption lasting > 6 weeks with the following exceptions:
 - Dosing interruptions to allow for prolonged steroid tapers to manage drug-related adverse events are allowed. Prior to re-initiating treatment in a subject with a dosing interruption lasting > 6 weeks, the Investigator must be consulted. Tumor assessments should continue as per protocol even if dosing is interrupted
 - Dosing interruptions > 6 weeks that occur for non-drug-related reasons may be allowed if approved by the Investigator. Prior to re-initiating treatment in a subject with a dosing interruption lasting > 6 weeks, the Investigator must be consulted. Tumor assessments should continue as per protocol even if dosing is interrupted
- Any adverse event, laboratory abnormality, or intercurrent illness which, in the judgment of the Investigator, presents a substantial clinical risk to the subject with continued nivolumab dosing

5.11

Definition of Dose Limiting Toxicity (DLT)

Dose-Limiting Toxicity will be graded according to the NCI Common Toxicity Criteria version4.03. See NCI Common Toxicity Criteria for definitions of DLT by organ system.

- a) All \geq grade 3 drug-related, clinically significant non-hematologic toxicities will be considered DLTs. A study drug-related occurrence of an elevation in AST/ALT $> 3 \times$ ULN and concomitant Bilirubin of $> 2 \times$ ULN is a Dose Limiting Toxicity and patients meeting this criteria should be permanently discontinued from study treatment (nivolumab).
As the following are common events in patients with leukemia (> 50%), they will not be used for the definition of MTD and DLT, nor will they be reported as ADRs: low blood pressure due to dehydration requiring fluid replacement, abnormalities of LDH (lactate dehydrogenase) and alkaline phosphatase, disturbances in electrolytes (magnesium, phosphorus,

calcium), alopecia, nausea and vomiting (if manageable with supportive care measures).

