7.0 Pretreatment Evaluation

- 7.1 History and physical examination, weight, BP.
- 7.2 CBC, platelet count, differential, creatinine, total bilirubin, SGPT, PT, PTT, INR, TSH.
Serum or urine pregnancy test for women of childbearing potential.
- 7.3 Bone marrow aspirate for morphology (within one month) and cytogenetics and molecular studies (if not done before).
- 7.4 Blood samples (10cc)/bone marrow, optional, for correlative studies.
- 7.5 Echocardiogram or MUGA scan.

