8.0 Evaluation During Study

- 8.1 CBC, platelet, differential (if WBC $> 10^9/L$) every 4-7 days during remission induction and every 1 to 4 weeks during maintenance therapy.
- 8.2 Bone marrow aspirate and cytogenetics and molecular studies (if abnormal at start) on day 21-28; then aspirate every 1-2 weeks as required until CR; then every 3-6 months in year 1 if deemed necessary by the treating physician. Bone marrow aspiration may be omitted in patients where there is clear evidence of active disease (e.g., persistent blasts in peripheral blood).
- 8.3 Creatinine, total bilirubin and SGPT, PT, PTT, and INR every 1-2 weeks during induction then every 4-8 weeks on study.
- 8.4 Blood samples (10cc)/bone marrow (optional studies, see Section 14)
- 8.5 End of Study: History and physical exam
End of study evaluation will be performed after the completion of the maintenance therapy, or any time before that if the patient withdraws from the study or the treatment is discontinued for toxicity or disease relapse/progression.

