13.2.3 Contraindications

Hypersensitivity to idarubicin, other anthracyclines, or any component of the formulation; bilirubin >5 mg/dl; pregnancy

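### The bilirubin waivers in section 4.5 have no ceiling, so a patient above 5 mg/dL can meet eligibility and be scheduled for idarubicin, which section 13.2.3 contraindicates at that level

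*Combined protocol and SAP*

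**What the plan says.** Section 4.5 (inclusion criteria) caps total bilirubin at 1.5 mg/dL. Two exceptions apply. The lead-in covers every laboratory limit in the list: "Serum biochemical values with the following limits unless considered due to leukemia". The bilirubin line adds its own: "unless increase is due to hemolysis or congenital disorder". Neither states how high a waived value may be.

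Section 5.2 gives the same idarubicin schedule for phase I and phase II: "Idarubicin 12 mg/m² IV over 15 to 30 minutes daily x 3 (days 1-3"). No bilirubin condition is attached.

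Section 13.2.3 lists the contraindications to idarubicin: hypersensitivity to it, "other anthracyclines, or any component of the formulation; bilirubin >5 mg/dl; pregnancy". There is no exception by cause. Section 13.2.4 adds general advice to lower the dose when liver function is impaired, without a threshold or an amount. Section 13.2 refers the reader to the package insert.

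On testing, section 7.2 requires before treatment "CBC, platelet count, differential, creatinine, total bilirubin, SGPT, PT, PTT, INR, TSH". Section 8.3 requires "Creatinine, total bilirubin and SGPT, PT, PTT, and INR every 1-2 weeks during induction", and the study calendar shows bilirubin weekly for four weeks in the first course.

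**The concern.** Eligibility expressly waives a laboratory limit that the drug section treats as absolute above a certain level. A site working from sections 4 and 5.2 can enrol a patient and schedule idarubicin from day 1 without meeting the threshold in section 13.2.3.

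The result is unsatisfactory however section 13 is read. If it is treated as background and not applied at entry, the patient may be given a contraindicated drug. If it binds, the trial enrols a patient who cannot receive part of the backbone that it is testing. What is at stake is the safety of a rare patient and the consistency of the entry rules.

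**Working it through.** The plan gives no figure to reproduce, and the check is a comparison of text. The one piece of arithmetic is the scheduled dose.

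**Step 1: follow a patient through the rules.** Take a baseline total bilirubin of 6 mg/dL attributed to leukemia, hemolysis or a congenital disorder.

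| Rule | Content | Result at 6 mg/dL |
|---|---|---|
| 4.5 limit | 1.5 mg/dL | Exceeded |
| 4.5 waivers | Leukemia, hemolysis or congenital cause; no ceiling | Limit waived |
| 4.10 to 4.23 | No exclusion names a bilirubin level | Not excluded by name |
| 5.2 | Idarubicin 12 mg/m² daily, days 1 to 3 | Scheduled |
| 13.2.3 | Contraindicated above 5 mg/dL | Contraindicated |

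The scheduled first-course dose is 12 mg/m² × 3 days = 36 mg/m², complete on day 3. The uncovered range is every waived value above 5 mg/dL.

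**Step 2: match the contraindications to the entry criteria.** Section 13.2.3 names three kinds. Pregnancy is dealt with in section 4.12. Hypersensitivity is dealt with in section 4.22, if its reference to study drug components includes idarubicin. Bilirubin has no matching exclusion, and it is the one that eligibility expressly waives.

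**Step 3: look for another rule that closes the gap.**
- Section 5.10.3 has numeric bilirubin limits, including "Total bilirubin > 5 x ULN" and a limit of 2 × ULN combined with raised AST or ALT. They apply to drug-related abnormalities and stop nivolumab.
- Section 5.11 uses the 2 × ULN combination as a dose-limiting toxicity: "patients meeting this criteria should be permanently discontinued from study treatment (nivolumab"). This also acts on nivolumab, which starts at about day 24, three weeks after the last idarubicin dose of the first course (24 − 3 = 21 days).
- Section 5.6 concerns myelosuppression. Section 5.7 needs a toxicity attributable to one of the drugs, not a raised baseline value.
- Section 5.9.2 reduces chemotherapy by 25% in subsequent courses only.
- Section 8.3 and the calendar require no bilirubin value between baseline and day 3, and no rule ties a result to idarubicin.

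The count of rules in sections 4 and 5 that set a bilirubin limit for starting idarubicin is therefore zero.

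**Step 4: check the baseline value.** Section 7.2 already requires total bilirubin before treatment, so the number needed exists. It sets no time window for chemistry, whereas section 7.3 asks for the marrow within one month. The baseline value may therefore not reflect day 1.

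**The case against.** The strongest reply is that the protocol already prints the prohibition. Section 13.2.3 states it, section 13.2.4 adds the hepatic precaution, and section 13.2 points to the package insert. A prescriber would have to overlook all three. Eligibility and prescribing are also separate steps: section 4.5 admits a patient but does not order a dose against a contraindication. Further discretion exists in section 4.11 (exclusion on the treating physician's judgment), in section 4.2 (patients over 60 must be judged fit for intensive chemotherapy) and, for phase II, in section 5.3 (other dose changes after discussion with the principal investigator). On this view the defect is where the text sits.

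Much of this stands, and it is why the point is minor. These safeguards lower the practical risk. None of them puts the 5 mg/dL threshold into an entry or dosing rule, and the discretionary ones name neither bilirubin nor idarubicin.

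It can also be said that the waiver is deliberate, because treating the leukemia may correct the bilirubin. That is reasonable between 1.5 and 5 mg/dL, and nothing here touches that range. Above 5 mg/dL, if treatment is intended, the protocol should say so, since section 13.2.3 currently says the opposite.

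A reader might infer more than the documents support:
- That patients will receive contraindicated idarubicin. The text shows only that they can be enrolled and scheduled.
- That everyone entering under the waiver needs a lower dose. Section 13.2.4 gives no threshold, and a value raised by leukemia, hemolysis or a congenital disorder need not mean impaired hepatic function.
- That dose-limiting toxicity attribution or the event-free survival analysis is affected. Nothing in section 12 depends on this point, and no number of affected patients is given.

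**Conclusion.** The concern holds as a minor inconsistency on a patient-safety point. The waivers in section 4.5 are uncapped, section 5.2 schedules idarubicin without a bilirubin condition, and section 13.2.3 contraindicates it above 5 mg/dL regardless of cause. No rule in sections 4 or 5 carries that threshold.

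The size in patients cannot be derived from the documents. I assume that very few would have a bilirubin above 5 mg/dL and also be offered intensive induction. The conclusion that such a patient can meet eligibility does not depend on that assumption; the low rating does, together with the safeguards outside sections 4 and 5. The 36 mg/m² is the planned exposure, not a measure of excess risk.

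**What to change.** State in section 4.5 that none of the waivers applies above a total bilirubin of 5 mg/dL, judged on the most recent pretreatment value under section 7.2 before day 1. Add to section 5.2 a cross-reference to sections 13.2.3 and 13.2.4.

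A cap at entry is preferable to a rule that admits the patient and holds idarubicin until bilirubin falls. A hold would need repeat values before dosing, and it would delay part of the treatment in a patient whose bilirubin is raised by the leukemia itself. That is a clinical trade-off which the documents cannot settle.

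The cost is about one line in each of two sections, by amendment. A very small number of patients with marked hyperbilirubinemia become ineligible until their value is 5 mg/dL or lower, and re-screening them needs a repeat routine bilirubin. They are patients to whom the protocol already says idarubicin should not be given. Sample size, monitoring rules and analysis are unchanged.
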